### 5.5.3.2 Other Secondary Efficacy Endpoints

#### 5.5.3.2.1 Convulsive Seizure Treatment Responders and Convulsive Seizure Freedom

The number of patients experiencing >25% increase,  $\geq 0$  to  $\leq 25\%$  increase, >0 to <25% reduction,  $\geq 25$  to <50% reduction,  $\geq 50$  to <75% reduction or  $\geq 75\%$  reduction in convulsive seizure frequency from baseline during the treatment period will be summarized by treatment group.

In addition to the key secondary endpoint, the proportion of patients considered treatment responders, defined as those with a  $\geq 25\%$  or  $\geq 75\%$  reduction in convulsive seizure frequency from baseline and the proportion of patients who are convulsive seizure free, defined as those with a 100% reduction in convulsive seizure frequency from baseline, during the treatment period, will be summarized by treatment group and analyzed using a CMH test stratified by age as described in Section 5.5.3.1.2.

Additionally, the proportion of patients responding will be presented graphically, by treatment arm, by plotting the percent reduction against the cumulative proportion of patients achieving that level of reduction. The x-axis will be the percent reduction from baseline and the y-axis will be the proportion of patients with at least that amount of reduction, i.e.  $y = \Pr(X \geq x)$ .

Sensitivity analyses will be performed on the ITT analysis set, repeating the above analysis, using data for the maintenance period only, and during each 4 weeks of the maintenance period (Week 1–4, Week 5–8 and Week 9–12 of the 12-week maintenance period).

Analyses on the maintenance period and by each 4 weeks of the maintenance period will include only patients who have at least 7 days of seizure data within each corresponding period.

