### 6.1 Inclusion Criteria

For inclusion in the study, patients must fulfil ALL of the following criteria:

- 6.1.1 Patient and/or parent(s)/legal representative must be willing and able to give informed assent/consent for participation in the study (see [Section 15.2](#)).
- 6.1.2 Patient and their caregiver must be willing and able (in the investigator's opinion) to comply with all study requirements.
- 6.1.3 Patient must be male or female aged between two and 18 years (inclusive).
- 6.1.4 Patient must have a documented history of DS which is not completely controlled by current AEDs.
- 6.1.5 Patient must be experiencing **four or more** convulsive seizures (i.e., tonic-clonic, tonic, clonic, atonic seizures) during the first 28 days of the baseline period.
- 6.1.6 Patient must be taking one or more AEDs at a dose which has/have been stable for at least four weeks.
- 6.1.7 All medications or interventions for epilepsy (including ketogenic diet and VNS) must have been stable for four weeks prior to screening and patient and caregiver are willing to maintain a stable regimen throughout the study. The ketogenic diet and VNS treatments are not counted as an AED.
- 6.1.8 Patient and/or parent(s)/legal representative is willing to allow his or her primary care practitioner and consultant to be notified of participation in the study.

- 6.1.9 Patient has completed their IVRS telephone diary on at least 25 days of the baseline period; patients who are non-compliant will be deemed ineligible to continue.

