## **5.1.1 Missing Data**

### **5.1.1.1 Handling of Missing Data for the Primary Efficacy Endpoint**

If a patient withdraws during the treatment period, then the primary analysis variable will be calculated from all the available data, during the treatment period, prior to the patient withdrawing.

Section 5.5.2.1 describes sensitivity analyses to account for missing data arising from unreported days in the Interactive Voice Response System (IVRS), and missing data arising from patients withdrawing during the treatment period.

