### 5.1.3.3 Treatment Period

The treatment period is defined as Day 1 to the earlier of:

- Day 99.
- The date of last dose as recorded on the 'End of Treatment Study Outcome' CRF page.

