### 5.2.2 Intention to Treat Analysis Set

All randomized patients who received at least one dose of IMP and have post-baseline efficacy data will be included and analyzed according to the treatment group to which they were randomized.

The intention to treat (ITT) analysis set is the primary analysis set for all efficacy endpoints.

Upon blinded review of the data, it was identified that 1 patient was randomized in error, but did not receive IMP. This patient will be excluded from the ITT analysis set.

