### 5.5.2 Primary Efficacy Endpoint

The primary endpoint is the change in convulsive seizure frequency during the treatment period (see Section 5.1.3.3) of the study compared to baseline (see Section 5.1.3.1) in patients taking GWP42003-P compared with placebo.

The primary endpoint will be analyzed using negative binomial regression on the sum of the convulsive seizure counts during the treatment period. However, convulsive seizure frequency (28-day average) and percentage change in seizure frequency will be presented using summary statistics. Percentage change from baseline in convulsive seizure frequency will be calculated as:

$$\frac{[(\text{Frequency during the treatment period} - \text{Frequency during baseline}) \div \text{Frequency during baseline}] \times 100}{}$$

The frequency during each period will be based on 28-day averages and calculated as:

$$(\text{Number of seizures in the period} \div \text{Number of reported days in IVRS in the period}) \times 28$$

For convulsive seizure endpoints only, if patients are randomized with no convulsive seizures during the baseline period then the percentage change from baseline will be calculated as:

---

(Frequency during the treatment period + 1) × 100

A mixed effect model with repeated measures will be performed modelling the observed number of convulsive seizures in the baseline period and treatment period implemented within the framework of general linear models using the negative binomial response distribution. The model will include stratified age group (2–5 years, 6–12 years and 13–18 years), time, treatment arm and treatment arm by time interaction as fixed effects and patient as a random effect. The log transformed number of days in which seizures were reported will be included as an offset. The time variable corresponds to an indicator for the baseline period and treatment period.

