### 5.5.2.1.1 Sensitivity Analysis of Missing Data

Missing data in this trial could potentially arise from the mechanism of MNAR. In order to understand the impact on the trial findings from missing data under the MNAR assumption, sensitivity analyses of the primary endpoint will be carried out for the ITT analysis set by multiple imputations on convulsive seizure frequency, based on time-points corresponding to each 14 days of the treatment period. The final period will consist of 15 days to include Day 99, if applicable.

For each 14 calendar days of the treatment period (15 days for the final period), the convulsive seizure frequency will be calculated as:

$$\left[ \frac{\text{Number of convulsive seizures in the period}}{\text{Total number of reported days in IVRS for all combined periods (maximum of 99 days)}} \right] \times 28$$

For patients with any periods with no reported days in IVRS, the total number of reported days in IVRS will include an additional 14 days for each missing period. For example, if a patient withdraws with 80 reported days in IVRS from 6 of the 7 14-calendar-day periods, then the total number of reported days in IVRS for the above calculation will be the sum of 80 and 14, i.e. 94 days.

Intermittent missing values for intermediate nominal visits before the last nominal visit will be imputed using the MCMC method in PROC MI with an IMPUTE=MONOTONE statement for 100 times for each treatment group separately. The resulting 100 partially imputed datasets will have a monotone missing pattern and will be further imputed under an MNAR assumption that the imputed value for the missing efficacy data of GWP42003-P patients (discontinued for certain reasons) are similar to, worse than, or better than those of placebo patients for the following 2 scenarios:

- (1) MNAR assumed for missing values resulting from discontinuation due to AEs in the GWP42003-P groups and Missing at Random (MAR) for others, including other patients discontinued in the GWP42003-P groups and patients in placebo group;
- (2) MNAR assumed for missing values resulting from discontinuation due to any reason or any other monotone missing data in the GWP42003-P groups and MAR for others, including patients in placebo group.

For each of the 2 scenarios above, imputation will be carried out once on each of the 100 imputed datasets using the SAS MI procedure (with the 100 imputed datasets included in the 'BY' statement of the MI procedure) as follows:

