#### 5.5.3.2.3 Non-Convulsive Seizures

Non-convulsive seizures will be summarized and analyzed as per the primary endpoint (Section 5.5.2). Patients with no non-convulsive seizures during the baseline period will be excluded from the analysis.

Sensitivity analyses will be performed on the ITT analysis set, repeating the above analysis, using data for only the maintenance period, and during each 4 weeks of the maintenance period (Week 1–4, Week 5–8 and Week 9–12 of the 12-week maintenance period).

Analyses on the maintenance period and by each 4 weeks of the maintenance period will include only patients who have at least 7 days of seizure data within each corresponding period.

Non-convulsive seizure responders and freedom will also be summarized and analyzed using the methods described in Section 5.5.3.2.1. Patients with no non-convulsive seizures during the baseline period will be excluded from the analysis.

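### In the main ITT analysis, seizure freedom has no completion or diary rule, so a patient who stops after a few quiet days counts as seizure free

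*SAP*

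**What the plan says.** SAP 5.5.3.2.1 counts as responders at the extreme those who are "convulsive seizure free, defined as those with a 100% reduction in convulsive seizure frequency from baseline, during the treatment period", and tests the proportion with a CMH test stratified by age. SAP 3.3.2.2 lists this among endpoints compared over the 14-week double-blind period.

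Three other sections determine how the definition works:

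- **Frequency** (SAP 5.5.2): "The frequency during each period will be based on 28-day averages and calculated as" seizures in the period divided by reported IVRS days in the period, times 28. No minimum number of days is set.
- **Window** (SAP 5.1.3.3): "The treatment period is defined as Day 1 to the earlier of" Day 99 and the date of last dose.
- **Population** (SAP 5.2.2): "All randomized patients who received at least one dose of IMP and have post-baseline efficacy data will be included".

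The rules on missing data do not reach this endpoint. On withdrawal, SAP 5.1.1.1 says: "If a patient withdraws during the treatment period, then the primary analysis variable will be calculated from all the available data". That concerns the primary endpoint only. So does SAP 5.5.2.1.1, where "sensitivity analyses of the primary endpoint will be carried out for the ITT analysis set by multiple imputations on convulsive seizure frequency". The missing-data rules for secondary endpoints (SAP 5.1.1.2) cover only the Epworth scale and the QOLCE.

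Protocol 6.1.9 sets a diary standard at baseline: "Patient has completed their IVRS telephone diary on at least 25 days of the baseline period". There is no counterpart for calling a patient seizure free on treatment.

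The definition is reused. SAP 5.5.3.2.3 states: "Non-convulsive seizure responders and freedom will also be summarized and analyzed using the methods described in Section 5.5.3.2.1". SAP 5.5.3.2.4 does the same for individual seizure types, and SAP Appendix 5 lists total-seizure freedom as Table 9.5.1.

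**The concern.** Taken together, these rules place a patient who takes IMP for a few days, reports no convulsive seizure and stops in the best outcome category of the trial. Such a patient has not shown freedom over 14 weeks; the seizures were simply not observed. A completer with a very sparse diary is treated in the same way.

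What is at stake is the seizure-free row, its difference in proportions and its CMH p-value, and the corresponding rows for non-convulsive, total and individual seizure types. If one arm has more early stopping than another, that arm's seizure-free percentage is raised by stopping rather than by treatment.

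**Working it through.** **Plan's own figure.** The plan gives no expected rate for seizure freedom. Its one design figure, 62 per group for at least 80% power (SAP 3.2), concerns a Wilcoxon comparison. Simulating from the two stated gamma distributions gives power 0.795 at 62 per group, which agrees within tolerance. Here 62 serves only as the arm size.

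**Step 1: apply the rule.** Three reported days, no seizures: (0 ÷ 3) × 28 = 0. Against any non-zero baseline the change is (0 − baseline) ÷ baseline × 100 = −100%. The patient is scored seizure free.

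**Step 2: chance of a quiet run with an unchanged rate.** Under a Poisson assumption, the probability of no seizure in d days at r per 28 days is exp(−r × d ÷ 28). At the entry minimum of 4 per 28 days (Protocol 6.1.5), 3 days gives exp(−0.429) = 65%, 7 days exp(−1) = 37% and 14 days exp(−2) = 14%. At an assumed 12 per 28 days the values are 28%, 5.0% and 0.25%.

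**Step 3: average over a population.** The documents give no withdrawal rate, stop timing or baseline median, so the following are assumptions:

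- baseline rate lognormal, median 8, 12 or 20 per 28 days, log-SD 1.0 or 1.2, kept if the baseline count is at least 4;
- no drug effect, and stopping independent of seizures;
- Poisson counts to the stop day, or to Day 99 for completers.

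The calculation is done with and without a patient-level change between periods, modelled as a gamma multiplier with shape 2.3059 and mean 1. The shape is the placebo value in SAP 3.2, but that section does not say which variable its gamma describes. Using it as a multiplier is therefore an inference.

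| Stop day (uniform) | Scored free, with multiplier | Without multiplier |
|---|---|---|
| Days 2–28 | 7.0–13.1% | 3.5–7.9% |
| Days 2–98 | 2.3–4.5% | 1.0–2.3% |
| Days 15–98 | 0.7–1.9% | 0.1–0.35% |
| Completers | 0.1–0.4% | about 0 |

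**Step 4: expected number in an arm of 62 at 10% stopping.** 62 × 0.10 = 6.2 stoppers.

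- Days 2–28: 6.2 × 0.035 = 0.2 to 6.2 × 0.131 = 0.8.
- Days 2–98: 6.2 × 0.010 = 0.06 to 6.2 × 0.045 = 0.3.
- Days 15–98: 6.2 × 0.001 = 0.01 (rounded) to 6.2 × 0.0186 = 0.12.

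**Step 5: inflation of the between-arm difference.** Bias = (difference in stopping rates) × (stopper rate − completer rate), for 10–15% against 2% stopping.

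- Days 2–28: 0.08 × 0.035 = 0.3 points to 0.13 × (0.1308 − 0.0036) = 1.65 points.
- Days 2–98: 0.08 × 0.010 = 0.1 to 0.13 × (0.0446 − 0.0036) = 0.5 points.
- Days 15–98: 0.08 × 0.001 = 0.01 to 0.13 × (0.0186 − 0.0036) = 0.2 points.
- Equal rates and timing: zero.

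**Step 6: sparse diaries.** Completers with only 7 reported days are scored free in 5–20% of cases under the same assumptions. The baseline standard carried over to treatment is 25 ÷ 28 = 89%, and 0.893 × 99 = 88.4 days.

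**Step 7: existing cover.** Maintenance starts on Day 15, so its 4-week blocks start on Days 15, 43 and 71. With 7 diary days required, the whole-maintenance and Weeks 1–4 analyses drop stops before about Day 15 + 6 = 21. The Weeks 5–8 analysis drops stops before about Day 43 + 6 = 49, and the Weeks 9–12 analysis before about Day 71 + 6 = 77. The PP repeat of convulsive freedom (Table 9.2.2) drops withdrawals (SAP 5.2.3). All of these exclude early stoppers; none counts them as not seizure free.

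**The case against.** The best defence is that the plan already surrounds this number with protection. A patient who stops on Days 2–28 is absent from the PP table and from the Weeks 5–8 and 9–12 analyses. IVRS compliance is summarized by arm (SAP 5.7.8), and listings of compliance, derived seizure data and disposition would let a reader find each early stopper scored as free. Using available on-treatment data is also consistent with the primary endpoint. Protocol 8.1.2 provides for suspending or amending dosing when an unacceptable AE occurs in titration, so very early stopping need not be typical.

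Most of this stands and limits the size of the problem. It does not remove it. The headline ITT row still counts the early stopper as a success, and a reader would have to rebuild the row from listings to see it. Appendix 5 lists no PP freedom table for total, non-convulsive or individual seizure types.

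A second objection is that completion is an imperfect cure: it makes freedom a composite of staying on treatment and having no seizures, and it does nothing for a completer with a sparse diary. Both points are fair. The first is a cost to disclose. The second is why the remedy also needs diary days reported and a diary-based sensitivity row.

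**Conclusion.** The gap is real and minor. As written, zero seizures over any number of reported days before stopping is tabulated and tested as seizure freedom in the main ITT analysis. Under the assumptions above the expected number of such patients is below one per arm at 10% stopping, and the between-arm inflation is about 0.01 to 1.7 points depending on when and how unequally patients stop. If patients stop because seizures persist, the figures would be lower.

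Four stronger readings are tempting and not supported:

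- **That a few false successes will decide the result.** In a single-stratum, uncorrected Mantel–Haenszel test, 4 of 62 against 0 of 62 gives p = 0.043 and 3 against 0 gives p = 0.081. Nothing in the documents makes counts of that size likely.
- **That the bias favours active treatment.** That needs more, and mostly early, stopping on active treatment. The documents give no stopping rates.
- **That the trial's main inference is affected.** The primary test does not use this definition, and seizure freedom is outside the hierarchy (SAP 3.3.2 and Table 3). The ≥50% responder endpoint, which is in the hierarchy, uses the same frequency. With the multiplier its difference moves by 0.3–0.8 points at 10–15% against 2% stopping on Days 2–28. That is not an upper bound, since it depends on the multiplier, so a sensitivity analysis is the proportionate response.
- **That the SAP contradicts the protocol.** Protocol 13.6.1 also ends the evaluable period no later than last IMP.

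**What to change.** In SAP 5.5.3.2.1:

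- Count a patient as convulsive seizure free over the treatment period only if the patient completed the treatment phase, as classed in the disposition summary (SAP 5.4.1), with no convulsive seizure reported. Keep non-completers in the denominator as not seizure free.
- Report the number of reported diary days behind each seizure-free classification. Add a sensitivity row that also requires at least 25/28 (89%) of treatment-period days reported, matching the baseline standard.
- State that the same rule applies to treatment-period freedom in SAP 5.5.3.2.3, SAP 5.5.3.2.4 and Table 9.5.1.
- Leave the responder main analyses and the cumulative plot unchanged, with a footnote that 100% reductions there include non-completers.
- Add one ITT sensitivity analysis of the ≥25%, ≥50% and ≥75% thresholds with treatment-period withdrawals as non-responders.

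The cost is SAP wording, one flag from completion status that is already summarized, one sensitivity table, a diary-based sensitivity row, and revised freedom rows in 11 ITT treatment-period tables (9.2.1, 9.5.1, 9.6.3 and the eight individual-type tables under 9.7). The PP table 9.2.2 is unaffected. The downside is that freedom becomes a composite of completing and having no seizures, so rates fall slightly, more in the arm with more withdrawals. The footnote is needed because a non-completer can then be a ≥75% responder, or sit at 100% on the plot, and yet not be counted as seizure free.

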#### 5.5.3.2.2 Status Epilepticus

The number of convulsive seizures greater than 30 minutes in duration and the number of non-convulsive seizures greater than 30 minutes in duration will be collected daily via IVRS.

The number of patients with convulsive and non-convulsive seizures greater than 30 minutes in duration, will be presented for the baseline and treatment periods.

In addition, the number of patients with any episodes post-baseline and no episodes during the baseline period, will be summarized by treatment group.

#### 5.5.3.2.3 Non-Convulsive Seizures

Non-convulsive seizures will be summarized and analyzed as per the primary endpoint (Section 5.5.2). Patients with no non-convulsive seizures during the baseline period will be excluded from the analysis.

Sensitivity analyses will be performed on the ITT analysis set, repeating the above analysis, using data for only the maintenance period, and during each 4 weeks of the maintenance period (Week 1–4, Week 5–8 and Week 9–12 of the 12-week maintenance period).

Analyses on the maintenance period and by each 4 weeks of the maintenance period will include only patients who have at least 7 days of seizure data within each corresponding period.

Non-convulsive seizure responders and freedom will also be summarized and analyzed using the methods described in Section 5.5.3.2.1. Patients with no non-convulsive seizures during the baseline period will be excluded from the analysis.

#### 5.5.3.2.4 Individual Seizure Types

For each individual seizure type (tonic-clonic, tonic, clonic, atonic, myoclonic, countable partial, other partial and absence seizures) summaries and analyses will be performed as per the primary endpoint (Section 5.5.2). Patients with no seizures during the baseline period, for a particular seizure type, will be excluded from the analysis of that seizure type.

Sensitivity analyses will be performed on the ITT analysis set, repeating the above analysis for tonic, tonic-clonic, atonic and clonic seizures only, using data for only the maintenance period, and during each 4 weeks of the maintenance period (Week 1–4, Week 5–8 and Week 9–12 of the 12-week maintenance period).

Analyses on the maintenance period and by each 4 weeks of the maintenance period will include only patients who have at least 7 days of seizure data within each corresponding period.

Individual seizure type responders and freedom will also be summarized and analyzed using the methods described in Section 5.5.3.2.1. However, the summaries and analyses during the maintenance period and during each 4 weeks of the maintenance period will be produced for tonic, tonic-clonic, atonic and clonic seizures only. Patients with no corresponding seizures, for a particular seizure type, during the baseline period will be excluded from the analysis for that seizure type.

In addition, the number of patients with an occurrence of an individual seizure type not experienced in the baseline period will be summarized by treatment group.

An occurrence of an individual seizure type not experienced in the baseline period is calculated as seizure types with no seizures experienced during the baseline period and at least one seizure experienced at any time post first dose of IMP.

#### 5.5.3.2.5 Caregiver Global Impression of Change in Seizure Duration

The CGICSD comprises the following question to be rated on a 3-point scale for each seizure type:

- Since the patient started treatment, please assess the average duration of the patient's seizures (comparing their condition now to their condition before treatment) using the scale below.

The 3 possible responses are:

- Decrease in average duration.
- No change in average duration.
- Increase in average duration.

The caregiver will be asked to assess the average duration of the patient's seizures at Visit 2 (prior to commencement of IMP) as a memory aid for assessment at the end of treatment visit.

Each response will be coded with a score from 1 to 3, where 1 = Decrease in average duration, and 3 = Increase in average duration.

For each seizure type, the CGICSD will be summarized by treatment group and analyzed using ordinal logistic regression.

Proportional odds modelling will be carried out by including treatment group and age group as factors. The estimated odds ratios (GWP42003-P groups vs. placebo), 95% CI for the odds ratios, and the p-values testing the null hypothesis that the odds ratio is equal to 1, will be presented.

